7.3 Withdrawal, Removal, and Replacement of Patients

A patient may voluntarily withdraw or be withdrawn from the study at any time for reasons including, but not limited to, the following:

- Unacceptable toxicity or AE
- Patient withdrawal of consent: At any time, a patient's participation in the study may terminate at his/her request. The reason for patient withdrawal will be noted in the electronic case report form (eCRF).
- Intercurrent illness: a condition, injury, or disease unrelated to the primary diagnosis that becomes apparent during treatment and necessitates the patient's termination from the study.
- General or specific changes in the patient's condition that renders him/her ineligible for further treatment according to the inclusion/exclusion criteria.
- Protocol deviation: The patient's findings or conduct fail to meet the protocol entry criteria or fail to adhere to the protocol requirements (e.g., treatment noncompliance, failure to return for defined number of visits). The deviation may necessitate premature termination from the study.
- Patient is administered any of the following prohibited therapies after enrollment into the study: parenteral corticosteroids, immunosuppressive agents, or cytotoxic agents (see Exclusion Criteria #7 and Exclusion Criteria #10 for exceptions to this exclusion); or any other investigational drug or device not utilized in this study.
- Lost to follow-up: The patient stops coming for visits, and study personnel are unable to contact the patient.
- Patient discontinuation on the basis of the Investigator's clinical judgment.
- This study may be terminated at the discretion of the Sponsor or any regulatory agency. An Investigator may elect to discontinue or stop the study at his or her site for any reason including safety or low enrollment.

Patients who withdraw or are withdrawn before completion of the Week 2 assessments and the Week 3 Wound-QoL questionnaire will be replaced to ensure that at least 52 patients will complete the study.

7.4 Follow-Up for Patient Withdrawal from Study

If a patient discontinues study treatment and is withdrawn from the study for any reason, the study site must immediately notify the medical monitor. The date and the reason for study discontinuation must be recorded on the eCRF. Patients who withdraw prematurely are to attend an early discontinuation visit, if possible, and complete all assessments.

In the event that a patient discontinues prematurely from the study due to a treatment-emergent AE (TEAE) or serious TEAE, the TEAE or serious TEAE will be followed until it resolves (returns to normal or baseline values) or stabilizes, or until it is judged by the Investigator to be no longer clinically significant.

Once a patient is withdrawn from the study, the patient may not re-enter the study. Patients who withdraw or are withdrawn before completion of the Week 2 assessments and the Week 3 Wound-QoL questionnaire will be replaced to ensure that at least 52 patients will complete the study.

8 TREATMENTS

8.1 Details of Study Product

Prontosan Wound Irrigation Solution is a clear, colorless liquid containing purified water, 0.1% undecylenamidopropyl betaine as a surfactant, 0.1% polyaminopropyl biguanide (polyhexanide [PHMB]) as a preservative, and sodium hydroxide for pH adjustment. The device is cleared by the FDA for prescription and over-the-counter use for cleaning wounds and for moistening and lubricating absorbent wound dressings for the management of cuts, lacerations, ulcers, burns, post-surgical wounds, and abrasions.^{7,8}

Prontosan Wound Gel is a clear, colorless gel containing glycerol, hydroxyethylcellulose, 0.1% undecylenamidopropyl betaine, 0.1% PHMB, and purified water. The device is cleared by the FDA for prescription and over-the-counter use for cleaning and moistening the wound bed and for the management of cuts, abrasions, lacerations, ulcers, first- and second-degree burns, partial and full thickness wounds, and surgical incisions. It can be used during wound dressing changes to soften encrusted wound dressings.^{18,19}

Commercially available Prontosan solution and commercially available Prontosan gel will be provided by the Sponsor for the study. Prontosan solution will be provided in 350-mL bottles and packed in cartons containing up to 10 bottles. Prontosan gel will be provided in 30-mL bottles and packed in cartons containing up to 20 bottles. Each carton will be labeled with the name and address of the Sponsor, the lot number, the expiration date, and will contain the product usage instructions. Cartons will be distributed to the study sites.

Storage

Prontosan solution and Prontosan gel are to be stored under controlled room temperature. Controlled room temperature is defined by the United States Pharmacopeia (USP) as 20 to 25°C (68 to 77°F) with allowed excursions between 15 to 30°C (59 to 86°F). Avoid storing these products in excessive heat, and do not refrigerate or freeze these products.

Use Prontosan solution and Prontosan gel prior to the expiration dates noted on the package labels. Prior to opening the bottle, the product is sterile by aseptic filtration (<1 CRU/mL), and the fluid and fluid path is nonpyrogenic prior to removal of the cap.

Each bottle is for single-patient use only. There is a shelf-life of 28 days after opening a bottle of Prontosan solution or Prontosan gel as long as the bottle is closed immediately after use, and the top of the bottle is protected from contamination or direct contact. Be sure to record the date opened on the designated space on the bottles.

Warnings

Prontosan solution and Prontosan gel are for external use only. Do not use for infusion or injection, and do not ingest.

Contraindications include the following: do not use on patients with a history of allergy to any of the ingredients, do not use in the presence of hyaline cartilage, and do not use in combination with anionic tensides (as these may impair preservation). Also, when removing soaps, lotions, ointments, oils, or enzymes from the wound, ensure that the entire wound is thoroughly rinsed with Prontosan solution.

8.2 Dosage Schedule

The frequency and method of application will be per the institutional guidelines and the Prontosan IFU for the individual patient wound(s). Prontosan solution and Prontosan gel are to be used according to these guidelines during the 4-week treatment period. Prontosan solution will be used to rinse and clean the wound(s) and the surrounding area; bandages or dressings may be soaked in the solution and/or the gel and used for cleaning as required. After the wound(s) has/have been cleaned (and in the clinic, measured and photographed), Prontosan gel will be applied directly as a 3-5 mm coating on shallow flat wound surfaces or deep wound fissures. Bandages or dressings will then be applied per institutional guidelines and Prontosan IFU.^{9,10}

When patients are at a clinic visit, the Investigator or designee will administer study treatment. At Weeks 1 and 2, the Investigator or designee will dispense enough Prontosan solution and Prontosan gel for the patient's treatment until the next study visit. The patient (and/or the patient's caregiver) will be trained to administer the treatment at home, and the patient will be given a diary and trained to record the date and time of each treatment and any reactions to treatment. Patients (and/or caregivers) will also be instructed to record the liquid level remaining after each use, and to return all used bottles and any unused bottles of study treatment at the next visit for product accountability.

8.3 Accountability and Compliance of Treatment

The Investigator or designee will maintain records of Prontosan solution and Prontosan gel delivered to the study site, the inventory at the site, the distribution to and use by each patient, and if approved, the on-site destruction of used and unused Prontosan solution and gel, or the return of materials to the Sponsor for storage or disposal. These records may include dates, quantities, lot numbers, expiration dates, and in-clinic temperature log.

Administration of study treatment in the clinic will be performed by the Investigator or designee, ensuring compliance with the individual patient's regimen.

At each visit after initiation of treatment, site staff will record compliance of patients with their assigned regimen. Patients will be instructed to bring their diaries and Prontosan bottles (used and unused bottles) back for inspection at each study visit. Patients are to be reminded of the importance of compliance with their assigned regimen, with an emphasis on administering their study treatment as they were instructed and staying on the schedule they were given for their wound care.

Used bottles and unused bottles must be returned at each visit, as compliance will be assessed by bottle usage. The Investigator or designee will record in the eCRF (yes/no) if the products were used correctly. Discontinuation for noncompliance is at the Investigator's discretion.

After accountability has been monitored for a completed or withdrawn patient, previously dispensed study product will be either given to the subject, returned to the Sponsor or destroyed on-site.

8.4 Medical History and Prior and Concomitant Medications

8.4.1 Medical History

Investigators should document prior significant illnesses that the patient has experienced prior to signing the ICF; this is the patient's medical history. New illnesses present after the ICF is signed and up to the time of first treatment (Week 1) are to be regarded as concomitant illnesses. Illnesses first occurring or detected during or after the first administration of study treatment and/or worsening of a concomitant illness during or after the first administration of study treatment are to be documented as AEs in the eCRF.

8.4.2 Prior and Concomitant Medications

Any medication or therapy that is taken by or administered to the patient during the course of the study must be recorded in the eCRF. Prior medications are defined as those taken by or administered to the patient before screening and up to the first study treatment. Concomitant medications are defined as those taken by or administered to the patient after the first study treatment. After the first treatment, medication to treat minor treatment-emergent illness is generally permitted; however, the following therapies are expressly prohibited throughout the study:

- Any antibiotic therapy for treatment of the wound. Antibiotic therapy for treatment of infections not related to the wound are acceptable.
- Oral, or parenteral corticosteroids, immunosuppressive agents, or cytotoxic agents (see Exclusion Criteria #7 for exceptions)
- Any investigational drug or device
- Any additional wound treatment topical solutions, including medicated dressings

At screening, if a patient has a wound infection that is being treated with one of these prohibited medications, the patient may be scheduled for a re-screening after the infection in the wound has cleared. At the re-screening, the patient must still meet all inclusion criteria and not exhibit any exclusion criteria, and the appropriate washout time for antibiotics (7 days) and/or for corticosteroids, immunosuppressive agents, and cytotoxic agents (30 days) must have been met prior to the first study treatment.

During the study, if a patient develops an infection in the wound(s) and requires treatment with a prohibited medication, the patient will be discontinued from the study. Patients who withdraw or are withdrawn before completion of the Week 2 assessments and the Week 3 Wound-QoL questionnaire will be replaced to ensure that at least 52 patients will complete the study.

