Chronic wounds often stall in the inflammation phase. Although they may differ in etiology, chronic wounds usually share some common features: elevated levels of proinflammatory cytokines, proteases, reactive oxygen species, and senescent cells; persistent infection; and a deficiency of stem cells and/or dysfunctional stem cells. Repeated tissue injury induces platelet-derived factors to stimulate the constant influx of immune cells; thus, the proinflammatory cytokine cascade becomes amplified and persists for a prolonged period, leading to elevated levels of proteases. Eventually, protease levels exceed the levels of their inhibitors, leading to the destruction of the extracellular matrix and the degradation of growth factors and their receptors. The destruction of the matrix not only prevents a progression to the proliferative phase, but also attracts more inflammatory cells, amplifying the inflammation cycle. Similarly, elevated levels of reactive oxygen species also damage the extracellular matrix, which stimulates proteases and inflammatory cytokines. This amplified inflammation cycle, together with the deficiency of functional stem cells, results in a failure to achieve complete re-epithelialization in tissue repair.^{3,4}

In caring for chronic wounds, the concurrent management of both the underlying systemic problem (e.g., diabetes, peripheral arterial disease) and the wound bed preparation encourages the proper environment in which autolytic tissue repair can take place. The basic tenets of wound bed preparation have been described by the TIME acronym: Tissue assessment and management, Infection/Inflammation management, Moisture imbalance

management, and Edge of wound observation and management.³ For tissue management, repetitive and maintenance debridement and wound cleaning are recognized as essential throughout the healing period. As almost all chronic wounds are thought to contain biofilms, topical antiseptics are commonly used to control bioburden in wounds. Excessive or insufficient wound exudate can be addressed with a wide range of dressings to regulate moisture balance, to protect peri-wound skin, and to optimize healing. At the edge of the wound, therapies such as negative pressure wound therapy may be used to help improve epithelial advancement and wound closure.⁵

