In a retrospective study of 110 patients with venous leg ulcers to examine clinical efficacy and cost-effectiveness, 57 patients were treated with Prontosan solution, and 53 were treated with Ringer's solution or normal saline solution. The wounds of the patients treated with Prontosan solution healed faster and in more cases (97% versus 89%). The Kaplan-Meier mean estimate (and associated standard error [SE]) demonstrated a statistically significant difference between groups ($p < 0.0001$) in time to healing. The mean time to healing in the Prontosan group was 3.31 months (SE=0.17) compared to 4.42 months (SE=0.19) in the Ringer's/saline group. Thus, with faster healing, using Prontosan solution was considered cost-effective.¹¹

A retrospective study was performed to assess the healing process of chronic and poorly healing wounds after the introduction of Prontosan solution and Prontosan gel to the standard of care at a municipal hospital in Germany (Municipal Hospital Bielefeld Mitte). The interventions added to the standard of care were routine irrigation of the wound with the irrigation solution at every dressing change and the additional application of the gel to every wound if there was no or only moderate exudate. The charts of 953 patients were analyzed 2 years after these changes were implemented. A total of 97% of patients had improved healing, with wound closure in 80% of these patients. Approximately two-thirds of patients found a great-to-complete reduction (improvement) in odor. In 29/953 (3%), a first or renewed wound infection developed after the beginning of treatment. A total of 99% had no pain or discomfort with Prontosan treatments; 1% experienced a slight burning sensation. On the basis of this analysis, the hospital continued the interventions as standard of care.¹²

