9.2.5 Week 5 (Final Visit: End of Treatment or Early Discontinuation)

At the Week 5 visit (final visit: end of treatment or early discontinuation), the following assessments will be performed by the Investigator or designee:

- Ask the patient to complete the Wound-QoL questionnaire before any other visit assessment.

- Review the diary and examine used bottles and any unused bottles of study treatment.
- Record concomitant medications.
- Measure vital signs (blood pressure, pulse, temperature).
- Collect blood for measuring HbA1c and for standard hematology and serum chemistry parameters.
- Perform a brief physical examination.
- Assess the wound(s) appearance, granulation tissue, exudate, drainage, surrounding erythema and/or swelling, and any signs of infection.
- Measure the wound(s) size pre-treatment (pre-debridement) with a standard, single-use, disposable ruler using the clock method (see Section 10.3 and Section 15, Appendix 2).
- Photograph the wound(s) pre-treatment (pre-debridement) using the study camera and a standard, single-use, disposable ruler to indicate relative size.
- Clean the wound(s) and wound area(s) with Prontosan solution per the institutional guidelines and Prontosan IFU for the individual patient wound(s).
- Assess the patient for any AEs.
- Measure the wound(s) size post-cleaning (post-debridement) with a standard, single-use, disposable ruler using the clock method.
- Photograph the wound(s) post-cleaning (post-debridement) using the study camera and a standard, single-use, disposable ruler to indicate relative size.
- Apply Prontosan gel to the wound(s) and apply the bandage/dressing per the institutional guidelines and the Prontosan IFU for the individual patient wound(s).

Patients who prematurely withdraw from the study for any reason should complete these early discontinuation visit requirements. If the early discontinuation visit is not done, the reason(s) will be recorded in the eCRF. Patients who withdraw or are withdrawn before completion of the Week 2 assessments and the Week 3 Wound-QoL questionnaire will be replaced to ensure that at least 52 patients will complete the study.

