4.2 Evaluable Population

The Evaluable Population includes all patients who receive at least 2 weeks of study treatment and complete the Week 3 Wound-QoL questionnaire.

The analyses of primary endpoint, secondary endpoints, and exploratory endpoints will be done in the evaluable population.

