5.1.6 Protocol Deviations

Protocol deviations will be listed as well as summarized and grouped into different categories such as

- Violation of inclusion/ exclusion criteria
- Time schedule deviations
- Non-compliance based on the investigator or designee's compliance records in eCRF.
- Missing essential data such as incomplete wound-QoL questionnaire data
- Patient not discontinued as per protocol of study (in case of infection or treatment with prohibited medication)
- Other non-compliance

Multiple deviations can occur in the same patient and thus a patient can be counted in more than 1 deviation category.

Patient listings of protocol deviations will include reasons for non-compliance and will be sorted by site.

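### A wound infection that needs a prohibited medication ends data collection, and the SAP gives no route for these patients' last Wound-QoL score into the Week 5 endpoint, so the single-arm change may lean toward improvement

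*Protocol*

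**What the plan says.** **Removal.** Protocol 8.4.2 directs that "if a patient develops an infection in the wound(s) and requires treatment with a prohibited medication, the patient will be discontinued from the study". Any antibiotic given for the wound is on its prohibited list. SAP 5.1.6 treats departure from the rule as a protocol deviation: "Patient not discontinued as per protocol of study (in case of infection or treatment with prohibited medication".

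**Replacement and population.** Under Protocol 8.4.2, "Patients who withdraw or are withdrawn before completion of the Week 2 assessments and the Week 3 Wound-QoL questionnaire will be replaced". The Evaluable population, used for the primary analysis, "includes all patients who receive at least 2 weeks of study treatment and complete the Week 3 Wound-QoL questionnaire" (SAP 4.2).

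**Last assessment.** Protocol 7.4: "Patients who withdraw prematurely are to attend an early discontinuation visit, if possible, and complete all assessments". Protocol 9.2.5 uses one procedure list for Week 5 and early discontinuation, and it opens with "Ask the patient to complete the Wound-QoL questionnaire before any other visit assessment".

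**Use of scores.** SAP 5.1.4 allows ±1 day around each visit from Week 2 to Week 5. Assessments outside the window are listed but do not enter the primary or secondary endpoints. SAP 5.1.2 covers missing questionnaire items and replacement, but not a missing Week 5 score. SAP 4.3 and 5.2.1 repeat the primary test in all treated patients.

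**The concern.** The primary objective is the change in quality of life after 4 weeks in patients with chronic leg wounds, tested against zero in one arm. Removal is triggered by something happening in the wound itself. The questionnaire asks about pain, smell, discharge and fear of worsening, so an infection that needs treatment could plausibly raise the score, and a higher score is worse. If so, the patients who supply a Week 5 score are partly selected for a better course, and there is no control group in which the same selection would cancel.

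The selection affects the estimate and its confidence interval as well as the p-value. It also cannot be repaired at analysis if the scores were not collected.

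**Working it through.** **1. The plan's own figure.** Inputs from Protocol 12.1: change 0.35, SD of differences 0.88, N = 52, two-sided 0.05, paired t-test. The noncentrality is 0.35/0.88 × √52 = 2.87. The noncentral t distribution gives 80.3% power, and 52 is the smallest N that reaches 80%. The stated sample size reproduces.

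**2. What happens to a removed patient's score.**

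| Time of removal | Replaced? | In Evaluable set? | Final Wound-QoL | Counts as Week 5? |
|---|---|---|---|---|
| Before the Week 3 form | Yes | No | Early discontinuation visit, if held | No mapping in the SAP; out of window |
| After the Week 3 form | No | Yes | Same | Same, unless the visit falls within 1 day of Week 5 |

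The Safety population brings the early cases back into the analysis set, but a paired t-test still needs a Week 5 value. Replacement restores the number of patients. It does not restore the missing scores.

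**3. Size.** Let p be the share of treated patients removed, r the mean change in the others and d the change that the removed patients would have shown at Week 5. Negative values are improvement.

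- Mean over all treated = (1 − p) × r + p × d
- Overstatement = p × (d − r)

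Assumptions:
- r = −0.35, the planning effect.
- d = 0 to +0.5. At the planning baseline of 3.53 on a scale that ends at 4, the largest possible mean worsening is 4 − 3.53 = 0.47, so +0.5 is slightly beyond that ceiling.
- p = 3% to 10%. The only infection figure in the documents is in Protocol 4.3: "In 29/953 (3%), a first or renewed wound infection developed after the beginning of treatment". It comes from a retrospective chart review, is not a 4-week rate, and counts infections whether or not they needed a prohibited medication. The 10% is purely an assumption.

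| p | d | Mean over all treated | Overstatement | Share of 0.35 |
|---|---|---|---|---|
| 3% | 0 | −0.3395 | 0.03 × 0.35 = 0.0105 | 3% |
| 3% | +0.47 | −0.325 | 0.03 × 0.82 = 0.025 | 7% |
| 3% | +0.5 | −0.3245 | 0.03 × 0.85 = 0.0255 | 7% |
| 10% | 0 | −0.315 | 0.10 × 0.35 = 0.035 | 10% |
| 10% | +0.47 | −0.268 | 0.10 × 0.82 = 0.082 | 23% |
| 10% | +0.5 | −0.265 | 0.10 × 0.85 = 0.085 | 24% |

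At 29/953, about 52 × 29/953 = 1.6 patients would be affected.

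**4. Effect on the test.** Suppose that the true mean change over all treated patients is zero and d = +0.47. The retained mean is then −p × 0.47/(1 − p), which is −0.015 at 3% and −0.052 at 10%. With 52 scored patients and SD 0.88, the chance of a significant result in the direction of improvement rises from 2.5% to 3.3% and 6.2% respectively.

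**The case against.** A reader might infer more than the documents support, in four ways.

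- *That no final score is collected.* One is planned, if possible, at the early discontinuation visit. The gap is in how the SAP uses it, and in the absence of a score at the patient's own Week 5 date.
- *That infection alone removes a patient.* Removal also requires the need for a prohibited medication. Protocol 4.1 names "persistent infection; and a deficiency of stem cells and/or dysfunctional stem cells" among the common features of chronic wounds, but this is background biology and not an event rate. Exclusion criterion 2 in Protocol 7.2 bars infected wounds at entry.
- *That replacement hides the failures.* SAP 5.1.5 lists discontinued patients with reasons, Table 1 in SAP 6 gives reasons for exclusion from populations, and SAP 5.2.6 counts treatment-emergent adverse events leading to discontinuation. Only withdrawals before the Week 3 form are replaced.
- *That the reported improvement is certainly too large.* No passage gives the quality-of-life change in infected patients, and a treated infection could have improved by Week 5.

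Two further points weigh against the concern. The objective speaks of change after 4 weeks of treatment, so scores taken off product answer a somewhat different question. SAP 5.1.1 also interprets the test in an exploratory sense only. Both points limit the weight of the finding. Neither explains why a planned score has no stated use, and exploratory status does not protect an estimate from selection.

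**Conclusion.** The point holds in conditional form. Followed as written, the plan leaves patients removed for a treated wound infection out of the paired comparison, whether or not they are replaced, and the Safety-population repeat does not bring them back. The result is biased toward improvement if these patients would have improved less than the rest. That is plausible but is an inference.

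Under the stated assumptions the overstatement is about 0.01 to 0.085 points. At 3% removal it is 0.01 to 0.03 points, which is minor. It grows in proportion to the rate, which the documents do not establish for this trial. The upper end needs an assumed 10% removal, a worsening of half a point and the loss of every such score. This is a cheap improvement of minor to moderate weight, not a defect that invalidates the study.

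**What to change.** The rule on when product is stopped stays as it is.

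1. **Protocol 7.3, 7.4 and 8.4.2.** Separate stopping product from ending data collection. Unless consent is withdrawn, collect the Wound-QoL at the patient's own Week 5 date, within the ±1 day window. Hand over a home form at the discontinuation contact and make one call, because blank forms are currently given out only at Week 2 and reminder calls cover only Weeks 3 and 4.
2. **SAP 5.2.1.** Use these scores in the Safety-population repeat of the primary analysis and report that result beside the Evaluable result.
3. **SAP 5.1.4.** State how an early discontinuation Wound-QoL score is used. Add a sensitivity analysis that assigns unfavourable values to infection withdrawals with no Week 5 score.
4. **SAP 5.1.6.** Reword the deviation category so that continued questionnaire collection is not counted as a deviation.
5. **Reconcile Protocol 7.3 with 8.4.2.** Section 7.3 makes withdrawal permissive and its list of prohibited therapies does not name wound antibiotics, whereas 8.4.2 makes discontinuation mandatory. The two passages must agree; which rule applies is for the sponsor to decide.

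Cost: a small protocol amendment, a few SAP sentences, and one extra form and call per affected patient. Some scores will come from patients off product, and the mean may be less favourable. The change has to be made prospectively, because uncollected scores cannot be recovered.
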